#### **8.6.** Administration

Subjects should be scheduled to begin study therapy following completion of Screening. E6201 will be administered at the dose level prescribed per protocol by IV infusion over 2 hours (± 10 minutes). In the Monotherapy Safety Run-in Phase, subjects received E6201 twice weekly on days 1, 4, 8, 11, 15 and 18 of a 28-day schedule. In the Combination Safety Run-in and Expansion Phases, subjects will receive E6201 twice weekly on days 1, 4, 8, 11, 15 and 18 of a 28-day schedule.

In the absence of lengthy clinical experience, E6201 should be considered an irritant and precautions should be taken to avoid extravasation. With IV administration of E6201, extravasation may occur with, or without an accompanying stinging or burning sensation (even if blood returns on aspiration of the infusion needle). If any signs or symptoms of extravasation occur, the infusion should be immediately terminated and restarted in another vein. The application of ice over the site of extravasation for approximately 30 minutes may be helpful in alleviating the local reaction.

E6201 must not be given by intramuscular or subcutaneous route.

#### 8.7. Dabrafenib

#### 8.7.1. Description

Dabrafenib mesylate (TAFINLAR) is an inhibitor of some mutated forms of BRAF kinases, including BRAF V600E, V600K, V600D. Dabrafenib also inhibits wild-type *BRAF* and CRAF kinases. Dabrafenib inhibits cell growth of various *BRAF* V600 mutation-positive tumors *in vitro* and *in vivo*.

Dabrafenib is supplied as 50 mg and 75 mg capsules for oral administration. Each 50 mg capsule contains 59.25 mg dabrafenib mesylate equivalent to 50 mg of dabrafenib free base. Each 75 mg capsule contains 88.88 mg dabrafenib mesylate equivalent to 75 mg of dabrafenib free base.

See the dabrafenib (TAFINLAR) U.S. Product Label for additional information on study drug description.

#### 8.7.2. Packaging and Labeling

See the dabrafenib (TAFINLAR) U.S. Product Label.

#### **8.7.3. Storage**

See the dabrafenib (TAFINLAR) U.S. Product Label.

#### 8.7.4. Administration

Subjects should be instructed to take dabrafenib at least 1 hour before or at least 2 hours after a meal. Doses should be approximately 12 hours apart. Subjects should be advised to avoid concurrent administration of strong inhibitors of CYP3A4 or CYP2C8. The subject may be advised

Confidential 44
December 31, 2019 Protocol Amendment 4

to read the FDA-approved patient labeling (Medication Guide) found in the TAFINLAR U.S. Product Label. See TAFINLAR prescribing information for additional information.

#### 8.8. Study Drug Accountability

The investigator must maintain accurate records of receipt of E6201 study drug, dispensing information, and the prompt return or destruction of unused supplies. A drug accountability log will be supplied to each clinical site for purposes of recording E6201 study drug dispensation for the study and will be monitored by Sponsor personnel. If the site has an electronic study drug accountability form that is in keeping with institutional practice and the form collects the same information as the form supplied by the Sponsor, this form may be substituted for the Sponsor's drug accountability form.

## 8.9. Study Drug Handling and Disposal

Unused or expired E6201 will be destroyed per institutional policy. Unused dabrafenib will be handled according to institutional policy.

Confidential 45
December 31, 2019 Protocol Amendment 4

#### 9. STUDY PROCEDURES

See Schedule of Study Procedures in APPENDIX D.

#### 9.1. Screening Procedures

The following evaluations are to be performed within 28 days of study treatment to determine subject eligibility:

- Administration of informed consent
- Medical history, physical examination and vital signs
- ECOG Performance Status
- Height and weight
- The following laboratory tests:
  - Hematology
  - Serum Chemistry
- Beta HCG pregnancy test for WCBP
- 12-lead ECG
- Review of concomitant medications
- Baseline CT or MRI of systemic and intracranial disease

## 9.2. Requirements During Treatment Cycle 1

#### 9.2.1. Cycle 1, Day 1

- Abbreviated physical examination
- Vital signs
- ECOG Performance Status
- Weight
- The following lab tests
  - Hematology, if not performed within previous 24 hours
  - Serum chemistry, if not performed within previous 24 hours
- E6201 study drug administration (Day 1 and Day 4)
- Begin twice daily dabrafenib treatment and provide Dabrafenib Patient Medication Diary to subject (applicable to Combination Phases of study only)
- 12-lead ECG, pre-dose, at 5 minutes after the infusion ends ( $\pm$  5 minutes)
- Review of concomitant medications

Confidential 46
December 31, 2019 Protocol Amendment 4

- Assessment of adverse events
- Assessment for survival

#### 9.2.2. Cycle 1, Day 8 ( $\pm$ 1 day)

- Vital signs
- ECOG Performance Status
- E6201 study drug administration (Day 8 and Day 11)
- Continue dabrafenib twice daily treatment
- Review Dabrafenib Patient Medication Diary with subject (applicable to Combination Phases of study only)
- Review of concomitant medications
- Assessment of adverse events
- Assessment for survival

#### 9.2.3. Cycle 1, Day 15 ( $\pm$ 1 day)

- Vital signs
- ECOG Performance Status
- E6201 study drug administration (Day 15 and Day 18)
- Continue dabrafenib twice daily treatment
- Review Dabrafenib Patient Medication Diary with subject (applicable to Combination Phases of study only)
- Review of concomitant medications
- Assessment of adverse events
- Assessment for survival

## 9.3. Requirements During Treatment Cycles After Cycle 1 (Cycle 2 and beyond) [± 3 days]

- Abbreviated physical examination (Day 1 only)
- Vital signs
- ECOG Performance Status
- Weight (Day 1)
- The following lab tests:
  - Hematology, if not performed within previous 24 hours

Confidential 47
December 31, 2019 Protocol Amendment 4

- Serum chemistry, if not performed within previous 24 hours
- E6201 study drug administration (Days 1, 4, 8, 11, 15 and 18)
- Continue dabrafenib twice daily treatment
- Review Dabrafenib Patient Medication Diary with subject (applicable to Combination Phases of study only)
- 12-lead ECG pre-dose, at 5 minutes after the infusion ends ( $\pm$  5 minutes)
- Review of concomitant medications
- Assessment of adverse events
- Assessment for survival
- CT or MRI of systemic and intracranial disease for re-staging (Day 28 of even numbered cycles, ± 7 days)

#### 9.4. At Relapse or Progression of Disease

- Disease assessment for response
- Review of concomitant medications
- Assessment of adverse events
- Assessment for survival

## 9.5. End of Treatment (28 Days After Last Dose of E6201 and/or Dabrafenib Study Medication ± 5 days)

- Physical examination
- Vital signs
- ECOG Performance Status
- Weight
- The following lab tests
  - Hematology
  - Serum chemistry
- 12-lead ECG
- Review of concomitant medications
- Assessment of adverse events
- Review Dabrafenib Patient Medication Diary (applicable to Combination Phases of study only)
- Assessment for survival

Confidential
December 31, 2019

## 9.6. Long-Term Follow-Up

Long-term follow-up will consist of a clinic visit or telephone call to assess survival every 3 months for up to 6 months.

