# 5.4. Duration of Study

Accrual is expected to be 24 months, with the last subject followed for up to 6 months. The total study duration is expected to be 30 months. The anticipated accrual rate is 1-2 subjects per month.

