#### 7. TREATMENT OF SUBJECTS

#### 7.1. **Description of Treatment Plan**

#### 7.1.1. **Treatment Duration**

Treatment will continue until confirmation of disease progression, unacceptable toxicity, or subject decision to discontinue therapy.

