#### 10.4.1.2. Secondary Efficacy Endpoints

To evaluate intracranial disease duration of response, duration of SD and time to progression of CNS metastases, progression-free survival and overall survival, as defined below:

- Duration of Response: length of time from the first evidence of objective response (CR, PR) of intracranial disease lesions to the first objective evidence of progression
- Duration of Stable Disease: length of time from first evidence of stable disease of intracranial disease lesions (CR, PR, SD) to for objective evidence of disease progression or death, whichever is earlier
- Time to Progression of CNS Metastases: length of time from date of first administration of study drug to first objective evidence of disease progression of intracranial lesions
- Progression-Free Survival: length of time from the date of first administration of study drug to the first objective evidence of disease progression or death, whichever is earlier
- Overall Survival: length of time from the date of first administration of study drug to the date of death from any cause.

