#### 11.3.2.2. Secondary Efficacy Endpoints

Non-CNS systemic disease response rates will be determined by RECIST v 1.1. For determination of intracranial disease duration of response, duration of stable disease and time to progression of CNS metastases, and for PFS and overall survival, the Kaplan-Meier product- limit method will be used to estimate the median survival. Subjects who do not have disease progression will be censored at the last follow-up time.

Confidential 58
December 31, 2019 Protocol Amendment 4

Duration of intracranial disease response or stable disease will be calculated from the date of first response or stable disease to the date of progression or death.

Time to progression of CNS metastases will be calculated from the date of first treatment to the date of first evidence of progression of intracranial lesions.

Progression-free survival will be calculated from the date of first treatment to the date of first evidence of progression or death.

Overall survival will be calculated from the date of first treatment to the date of death from any cause; subjects who do not experience death will be censored at the last follow-up time.

SAS Version 9.3 for Windows (SAS Institute, Cary, NC) or higher will be used for all analyses.

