## APPENDIX D. SCHEDULE OF STUDY PROCEDURES

Study Activity	Screening a	Treatment Cycle 1		Treatment Cycles after Cycle 1		Progression or Relapse	End of Treatment l	Long-Term Follow-Up n	
		Day 1	Day 8 i	Day 15 i	Day 1	End of Cycle 2 j,k			
Signed ICD	X								
Medical History	X								
Physical Examination	X	X			X h			X	
Vital Signs	X	X	X	X	X			X	
ECOG Perform. Status	X	X	X	X	X			X	
Height	X								
Weight	X	X			X			X	
Hematology b	X	X			X			X	
Serum Chemistry c	X	X			X			X	
Beta-hCG for WCBP	X								
12-lead ECG	X	X d			X d			X	
Concomitant Medications	X	Continuous							
AE Assessment		Continuous							
Disease Assessment e	X					X	X		
E6201 Administration f		X (+D4)	X (+D11)	X (+D18)	X (D 1, 4, 8, 11, 15, 18)				
Dabrafenib Dosing g,m		X	X	X	X			X m	
Assessment of Survival		X			X	X	X	X	X

- a Screening to be performed within 28 days of Cycle 1, Day 1
- b Hematology parameters collected at Screening, Cycle 1 Day 1 (only if not performed in the previous 24 hours), Day 1 of each subsequent cycle (within 3 days of Day 1 of each subsequent cycle) and End of Treatment. See Table 9 for tests to be conducted at each time point.
- c Serum chemistry collected at Screening, Cycle 1 Day 1 (only if not performed within the previous 24 hours), Day 1 of each subsequent cycle (within 3 days of Day 1 of each subsequent cycle) and End of Treatment. See Table 9 for tests to be conducted at each time point.
- d ECGs performed pre-dose and at the end of the E6201 2-hour infusion (± 5 minutes)
- e Disease Assessment may include CT, MRI, and/or physical exam
- f E6201 IV twice weekly Day 1,4, 8, 11, 15 and 18 of each 28-day cycle
- g Dabrafenib dose orally twice daily, continuously. Provide Dabrafenib Patient Medication Diary.
- h Abbreviated physical exam
- i Day 8, 15 ( $\pm 1$  day)
- j Day 28 (±7 days)
- k Perform at the end of every even numbered cycle thereafter
-  End of Treatment visit should be within 28 days from last dose of study medication (±5 days)
- m Review Dabrafenib Patient Medication Diary (each clinic visit + End of Treatment)
- n Long-term follow-up for 6 months consists of clinic visits or telephone calls every 3 months to assess survival status

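### Survival contact is capped at 6 months, apparently from End of Treatment, so overall survival censoring depends on time to progression and the later Kaplan-Meier curve is likely, not certainly, too high

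*Combined protocol and SAP*

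**What the plan says.** OS is a secondary objective (Section 4.2). Section 10.4.1.2 defines it as "length of time from the date of first administration of study drug to the date of death from any cause". Section 11.3.2.2 states that "the Kaplan-Meier product- limit method will be used to estimate the median survival", and that "subjects who do not experience death will be censored at the last follow-up time". It gives no common cut-off date and no sensitivity analysis for censoring related to prognosis.

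Three places govern how long survival is observed:

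- Section 9.6 sets contacts "to assess survival every 3 months for up to 6 months". It does not say from when.
- Appendix D, footnote n: "Long-term follow-up for 6 months consists of clinic visits or telephone calls every 3 months to assess survival status". This belongs to the last column of the schedule, after the End of Treatment column. The End of Treatment visit (Section 9.5) is 28 days after the last dose, plus or minus 5 days.
- Section 5.4 expects 24 months of accrual with up to 6 months for the last subject, and adds: "The total study duration is expected to be 30 months".

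Section 7.1.1 fixes what ends treatment: "Treatment will continue until confirmation of disease progression, unacceptable toxicity, or subject decision to discontinue therapy".

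**The concern.** Kaplan-Meier requires that a subject censored at time t has the same later risk of death as those still under observation at t. Section order and the schedule columns suggest that the 6-month limit starts at End of Treatment. On that reading, an event that carries prognosis, usually progression, starts the censoring clock. A subject who progresses at month 2 and is alive at month 9 leaves the OS risk set. A subject still on treatment at month 9 stays in it. Beyond about 7 months the risk set therefore contains too few subjects who have stopped treatment. If their death risk is higher than that of subjects on treatment, the curve is too high.

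The monotherapy phase shows the practical effect. Section 3.4.1 reports that all 4 subjects had discontinued by this amendment, dated December 31, 2019. Even if the last dose had been on that date, 28 days plus 6 months ends contact in July 2020. The synopsis puts completion at April 2021. Any of them still alive would go uncontacted for about 9 months of an open study.

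At stake is a descriptive secondary endpoint. Deaths that nobody asks about are not observed.

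**Working it through.** **The plan's own figure.** Accrual 24 + last subject 6 = 30 months, as Section 5.4 states. This does not fit a limit that starts at End of Treatment. A subject entering at month 24 would be due contact until 24 + time on treatment + 28 days + 6 months, which is past month 30. The sections need reconciling whatever the size of the bias.

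**Inputs.** From the documents: 24 months of accrual, closure at month 30, and contact ending c = 6 months + 28 days = 6.9 months after treatment end (the implied start point). Assumed, because the documents give no figures: exponential time on treatment to progression, with rate a = ln 2 / median, and exponential survival afterwards, with rate b = ln 2 / median, independent of time on treatment.

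**Formulas.**

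- On treatment at t: exp(-at).
- Alive off treatment at t, everyone followed: a × ∫ exp(-ap) exp(-b(t-p)) dp, for p from 0 to t.
- Alive off treatment and still contacted: the same integral, for p from max(0, t-c) to t.
- Hazard that Kaplan-Meier sees: b × off / (on + off).

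Up to t = c the two integrals are identical, so the curve before about 7 months is unaffected.

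**One point by hand.** Medians 4 and 6 months give a = 0.1733, b = 0.1155 and a/(a-b) = 3. At t = 12:

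- On treatment: 0.125.
- Off treatment, everyone followed: 3 × (0.250 - 0.125) = 0.375. Off-treatment share 0.375/0.500 = 75%; hazard 0.1155 × 0.75 = 0.087 per month.
- Off treatment under the limit: 3 × (0.250 × 0.746 - 0.125) = 0.184. Share 0.184/0.309 = 60%; hazard 0.1155 × 0.596 = 0.069 per month.

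The hazard at month 12 is understated by about a fifth. Carried through the curve, median OS reads 12.7 instead of 12.0 months, and 18-month OS 34.7% instead of 28.7%.

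**Range of median OS (months).** The last two columns add a constant death hazard on treatment. Each difference is taken against the true median under that hazard.

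| Median to progression + median afterwards | True | Under the limit | Difference | Difference, 0.02/month | Difference, 0.05/month |
|---|---|---|---|---|---|
| 2 + 3 | 6.0 | 6.0 | 0.0 | 0.0 | 0.0 |
| 3 + 4 | 8.4 | 8.5 | 0.1 | 0.0 | 0.0 |
| 4 + 6 | 12.0 | 12.7 | 0.7 | 0.3 | 0.1 |
| 6 + 6 | 14.5 | 16.3 | 1.8 | 0.6 | 0.1 |
| 4 + 9 | 15.2 | 17.0 | 1.8 | 0.7 | 0.1 |
| 6 + 9 | 18.0 | 21.7 | 3.7 | 1.2 | 0.2 |

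With no on-treatment deaths, 28% to 43% of subjects in the last four rows are censored alive by the limit before month 30. A 12-month median after progression is a more extreme assumption. With a 6-month median to progression it gives 26.9 against 21.2 months.

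**Other hazard patterns (simulation, 400,000 subjects per scenario).**

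- Early progressors also die faster afterwards: the overstatement reaches 14.0 points at 18 months and 6.9 months in the median.
- 40% long survivors after treatment end: 18-month OS is too low by 1.2 to 9.1 points.
- Early progressors live longer after stopping: 12-month OS is too low by 0 to 14.7 points.

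**With the fix.** When everyone is followed to the common month-30 closure, the median is within 0.1 month of truth, and 12- and 18-month OS within 0.2 points, in every scenario.

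**The case against.** A reader might infer that the protocol fixes the cut-off at 6 months after each subject's own treatment end, and that OS is therefore biased upward. The documents do not support either statement as fact. Section 9.6 and footnote n name no start point, and Section 5.4 can be read as follow-up of everyone to a common closure. The direction is conditional too. Subjects censored by the limit have already survived about 7 months off treatment, so they are a selected group and need not have the highest death risk. The patterns with the reversed sign show this.

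The larger figures also depend on favourable simplifications. They assume no deaths on treatment, although the PFS definition counts death. They use true medians of 12 to 18 months, while eligibility asks only for a life expectancy of at least 3 months, and Section 3.2.1 cites 1 to 3 months under supportive care or steroids. Neither is a forecast for the combination, but shorter survival belongs in the range, and there the error vanishes.

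The calendar matters as well, because efficacy is analysed separately for the combination phases. If their enrolment starts about the amendment date (an assumption), accrual lasts about 10.5 months and closure comes at about month 16. Then 15% to 25% are censored by the limit, and a true median of 18 months is not reached even with full follow-up.

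It would also be too strong to say that no analysis could repair the loss. Under independent exponentials, time to progression and the first 7 months afterwards identify OS parametrically, but only if that model is right.

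Finally, OS carries no test or decision rule here, and with about 18 subjects sampling error will exceed the bias.

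All of this limits the size and certainty of the point. It does not remove the dependence of censoring on progression when the limit is applied from End of Treatment, nor the conflict between the sections.

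**Conclusion.** The point holds in conditional form. If the limit runs from End of Treatment, as the layout implies, OS censoring depends on time to progression, and the Kaplan-Meier curve beyond about 7 months is informatively censored. The bias is likely upward, because death risk is usually higher after progression than on treatment, but the documents do not establish that.

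For assumed medians of 2 to 6 months to progression and 3 to 9 months afterwards, the error in median OS runs from nil to about 3.7 months. It is nil when the true median is about 6 months. It is under 0.2 month with an on-treatment death hazard of 0.05 per month, and at most about 1.2 months at 0.02. The upper end needs 6 plus 9 months with no on-treatment deaths. None of these values is a prediction for this trial.

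The primary intracranial response analysis is unaffected. The change is worth making because the remedy is cheap and uncollected survival status may not be recoverable later.

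**What to change.** Reconcile Sections 5.4 and 9.6 and Appendix D footnote n:

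- State the event from which long-term follow-up starts.
- Continue survival contact every 3 months until death, withdrawal of consent or one common study-close date within the planned study period, in place of the 6-month limit per subject.
- In Section 11.3.2.2 and the synopsis, censor OS at the last date known alive, up to that common cut-off.

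The cost is a few more telephone calls per surviving subject. There is no new procedure, no change to treatment and no longer trial. Subjects whose 6 months have already ended, including any surviving monotherapy subjects, would need one contact to update their status, if their consent allows it.

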#### 10. DESCRIPTION OF ASSESSMENTS

#### **10.1.** Safety Assessments

Safety will be assessed through the monitoring of adverse events (AEs), clinical laboratory parameters (hematology, serum chemistry), vital sign measurements, ECGs and physical examinations. Adverse events will be classified according to the Medical Dictionary for Regulatory Affairs (MedDRA) and graded according to the National Cancer Institute Common Terminology Adverse Event (NCI CTCAE) version 4.03.

#### **10.2.** Safety Parameters

#### 10.2.1. Vital Signs

Vital sign measurements include temperature, blood pressure and pulse rate. Additional measurements may be obtained if clinically indicated. Any value considered clinically significant by the investigator will be recorded as an AE on the CRF. Clinically significant changes compared to baseline values should be followed until clinical resolution.

#### 10.2.2. Weight and Height

Weight will be measured at Screening, Day 1 of each treatment cycle, and the End of Treatment Visit. Height will be measured at screening.

#### 10.2.3. Physical Examination

Complete physical examinations include the following body system evaluations: General Appearance, Skin, Musculo-skeletal, Eyes, Ears, Nose, Throat, Cardiovascular, Chest, Abdomen, Lymph Nodes, and Neurological. Symptom-oriented (abbreviated) evaluations will be performed at study visits where indicated, and otherwise when clinically indicated.

#### 10.2.4. Electrocardiogram (ECG)

ECGs will be taken within 28 days prior to Cycle 1 Day 1, pre-infusion, 5 minutes following the end of the E6201 2-hour infusion, Day 1 of every cycle thereafter (pre-infusion and 5 minutes following the end of the infusion), and at the End of Treatment visit.

#### **10.2.5.** Laboratory Assessments

Clinical laboratory tests include hematology and serum chemistry (Table 9).

Confidential 50
December 31, 2019 Protocol Amendment 4

